18.0 Quality control and audit

Steps to be taken to ensure the accuracy and reliability of data include the selection of qualified investigators and appropriate study centers, review of protocol procedures with the investigator and associated personnel before the study and periodic monitoring visits by the sponsor. Written instructions will be provided for administration and collection of study questionnaires.

Guidelines for CRF completion will be provided and reviewed with study personnel before the start of the study. The sponsor will review CRFs and patient questionnaires for accuracy and completeness during on-site monitoring visits and after transmission to the sponsor; any discrepancies will be resolved with the investigator or designee, as appropriate. After upload of the data into the clinical study database they will be verified for accuracy and consistency with the data sources.

The study will be performed following the IMS and AbbVie Standard Operating Procedures (SOPs) for Observational Studies.

19.0 Communication of findings

AbbVie / IMS shall retain ownership of all screeners, case report forms, data analysis, and reports which result from this study.

All information obtained as a result of the study will be regarded as confidential, until appropriate analysis and review by AbbVie and the investigator(s) are completed. The results of the study may be published or presented by the investigator(s) after the review by, and in consultation and agreement with AbbVie, such that confidential or proprietary information is not disclosed.

Prior to publication or presentation, a copy of the final text should be forwarded by the investigator(s) to AbbVie for comment. Such comments shall aim to ensure the scientific content of the proposed publications and/or presentations and ensure that the data and material receive fair, accurate, and reasonable presentation.

Appendix B. Inclusion/Exclusion Form

1023250 Real-World Impact of RA					
Site number	Participant ID				

Patient Inclusion/Exclusion Form

Today's date: / / Month Day Year

Please check if the patient meets all of the following inclusion criteria.

 Subject has a diagnosis of RA as defined by the 1987 revised ACR classification criteria and/or the ACR/EULAR 2010 classification criteria (any duration since diagnosis) 	 Yes  No

 Male or female subject ≥ 18 years of age (local definition according to adalimumab label) who is in compliance with eligibility for adalimumab based on the local label 	 Yes  No

 With moderate to severe RA defined as DAS28 (ESR) or DAS28 (CRP) > 3.2 	 Yes  No

 Biologically treatment naïve and initiated adalimumab at baseline visit 	 Yes  No

 Availability of clinical data of the previous 12 weeks prior to baseline 	 Yes  No

 Ability to self-complete patient questionnaires 	 Yes  No

 Subject must be able and willing to provide written informed consent and comply with the requirements of the study protocol 	 Yes  No

The patient can only be enrolled with 'Yes' checked for all inclusion criteria above.

Please check if the patient meets any of the following exclusion criteria.

 The patient is pregnant or breast feeding at enrolment or wishes to become pregnant in the next 24 weeks 	 Yes  No

 Participation in any RA-related clinical trial at the time of enrolment, at baseline or at any point during the past 24 weeks prior to baseline 	 Yes  No

 The patient, who in your view, may not be able to accurately report their quality of life or prior resource utilization 	 Yes  No

 The patient, who in your view, may not be able to adhere to adalimumab therapy over 24 weeks 	 Yes  No

The patient can only be enrolled with 'No' checked for all exclusion criteria above.

Appendix C. Clinical Case Report Form (CRF)

Baseline:

1023259 Real-World Impact of RA
____ - ____
Site number Participant ID

Clinician Case Report Form (Baseline)

All of the following information must be completed by the clinician or his/her representative.

Clinician name: _____

Clinician signature: _____

[figure not shown]
Patient ID	

____	____	

Site #	Participant #	

	____	____	Site #	Participant #														
____	____																		
Site #	Participant #																		
Today's date	

____	____	/	____	____	/	____	____	____	

Day	Month		Year						

	____	____	/	____	____	/	____	____	____	Day	Month		Year					
____	____	/	____	____	/	____	____	____											
Day	Month		Year																

Please provide the information below.

1. When was the patient diagnosed with Rheumatoid Arthritis?	

____	____	____	____	

Year	

	____	____	____	____	Year			
____	____	____	____						
Year									
2. What is the patient's current disease status?	 Moderate  Severe								

1023259 Real-World Impact of RA
 -
 Site number Participant ID

imshealth™
 INTELLIGENCE APPLIED.

Please provide the information below.		
3. Please perform a swollen and tender joint examination on your patient using the figure below and record the total number of tender/swollen joints in the appropriate boxes on the right.	  Tender Joint Count	  Swollen Joint Count
If diagnosis is RA:		
4. Please record the most recent Erythrocyte Sedimentation Rate (ESR) (in mm/hour) or C-reactive protein (CRP) (in mg/L) of this patient.	  ESR (mm/hour) Test Date (DD/MM/YYYY): ____/____/_____	
	  CRP (mg/L) Test Date (DD/MM/YYYY): ____/____/_____	
5. Please record the latest DAS28 score*, if calculated		

* For calculation instruction, please refer to study protocol, page 21, clinical case report form (CRF).

1023259	Real-World Impact of RA
Site number	Participant ID

6. Please check all the comorbidities this patient has currently.

- No comorbidity
- Myocardial infarction
- Congestive heart failure
- Peripheral vascular disease
- Cerebrovascular disease
- Dementia
- Chronic pulmonary disease
- Connective tissue disease
- Ulcer disease
- Mild liver disease
- Diabetes
- Hemiplegia
- Moderate or severe renal disease
- Diabetes with end-organ damage
- Any tumor
- Leukemia
- Lymphoma
- Moderate or severe liver disease
- Metastatic solid tumor
- AIDS

1023259 Real-World Impact of RA

Site number	-	Participant ID
-------------	---	----------------

7. Please check all the prior medications this patient has received for her/his Rheumatoid Arthritis in the last 6 months.
(No response option for biologics is given as the current study recruits only patients with no history of any biologics prior to the study).

Drug Name	Average number of pills per day	Dose strength	Times per month
Disease Modifying Antirheumatic Drug (DMARD)			
 ₁ Auranofin (Ridaura, Myochrysine)	_____	_____ mg	_____
 ₂ Azathioprine (Imuran)	_____	_____ mg	_____
 ₃ Cyclosporine (Sandimmune and Neoral)	_____	_____ mg	_____
 ₄ Hydroxychloroquine (Plaquenil)	_____	_____ mg	_____
 ₅ Leflunomide (Arava)	_____	_____ mg	_____
 ₆ Methotrexate (Rheumatrex, Folex)	_____	_____ mg	_____
 ₇ Minocycline (Minocin, Dynacin and Vectrin)	_____	_____ mg	_____
 ₈ Sulfasalazine (Azulfidine)	_____	_____ mg	_____
 ₉ Others	_____	_____ mg	_____
Anti-inflammatory Drug (NSAID)			
 ₁₀ Ibuprofen (Advil, Motrin, Nuprin)	_____	_____ mg	_____
 ₁₁ Naproxen (Naprosyn, Anaprox, Aleve)	_____	_____ mg	_____
 ₁₂ Celecoxib (Celebrex)	_____	_____ mg	_____
 ₁₃ Aspirin (ASA)	_____	_____ mg	_____
 ₁₄ Diclofenac (Voltaren)	_____	_____ mg	_____
 ₁₅ Indomethacin (Indocid)	_____	_____ mg	_____
 ₁₆ Others	_____	_____ mg	_____
Others			
 ₁₇ Steroids	_____	_____ mg	_____
 ₁₈ Stomach or gastric medications	_____	_____ mg	_____

1023259 Real-World Impact of RA
____ - ____
Site number Participant ID

8. Please check all the prior surgeries this patient has received for her/his Rheumatoid Arthritis in the last 6 months.			
 No surgery performed			
 Yes →	Type of Surgery (Please input the number of the list below)	Length of Stay*	Date of Surgery (DD/MM/YYYY)
 1	_____	____ days	____/____/____
 2	_____	____ days	____/____/____
 3	_____	____ days	____/____/____
 4	_____	____ days	____/____/____
 5	_____	____ days	____/____/____
List of common surgeries for rheumatoid arthritis:			
1. Arthroscopy 2. Carpal tunnel release 3. Cervical spinal fusion 4. Total knee replacement 5. Total hip replacement 6. Knee arthrodesis (fusion) 7. Hip arthrodesis (fusion) 8. Synovectomy 9. Other: _____			

* For day surgeries, please input 0 days.

1023259 Real-World Impact of RA
____ - ____
Site number Participant ID

[figure not shown]

9. Please check any Hylan G-F 20 (Synvisc) injection this patient has received for her/his Rheumatoid Arthritis in the last 6 months.

 No injection performed	Injection Place	Dosage	Number of Shots
 Yes →	 Hip	____ ml	____
	 Knee	____ ml	____

10. Please provide the dosing information for the first injection of Adalimumab (Humira) this patient has received for her/his Rheumatoid Arthritis.

First time administration (DD/MM/YYYY):	Dosage
____/____/____	____ mg

11. Please record the current medications this patient has received for her/his Rheumatoid Arthritis.			
Drug Name	Average number of pills per day	Dose strength	Times per month
Disease Modifying Antirheumatic Drug (DMARD)			
 ₁ Auranofin (Ridaura, Myochrysine)	_____	_____ mg	_____
 ₂ Azathioprine (Imuran)	_____	_____ mg	_____
 ₃ Cyclosporine (Sandimmune and Neoral)	_____	_____ mg	_____
 ₄ Hydroxychloroquine (Plaquenil)	_____	_____ mg	_____
 ₅ Leflunomide (Arava)	_____	_____ mg	_____
 ₆ Methotrexate (Rheumatrex, Folex)	_____	_____ mg	_____
 ₇ Minocycline (Minocin, Dynacin and Vectrin)	_____	_____ mg	_____
 ₈ Sulfasalazine (Azulfidine)	_____	_____ mg	_____
 ₉ Others	_____	_____ mg	_____
Anti-inflammatory Drug (NSAID)			
 ₁₀ Ibuprofen (Advil, Motrin, Nuprin)	_____	_____ mg	_____
 ₁₁ Naproxen (Naprosyn, Anaprox, Aleve)	_____	_____ mg	_____
 ₁₂ Celecoxib (Celebrex)	_____	_____ mg	_____
 ₁₃ Aspirin (ASA)	_____	_____ mg	_____
 ₁₄ Diclofenac (Voltaren)	_____	_____ mg	_____
 ₁₅ Indomethacin (Indocid)	_____	_____ mg	_____
 ₁₆ Others	_____	_____ mg	_____
Others			
 ₁₇ Steroids	_____	_____ mg	_____
 ₁₈ Stomach or gastric medications	_____	_____ mg	_____

Thank you for completing the Clinician Case Report Form.
Please return this form to the IMS representative.

Follow-up:

1023259 Real-World Impact of RA

Clinician Case Report Form (Follow-up)

All of the following information must be completed by the clinician or his/her representative.

Clinician name: _____

Clinician signature: _____

[figure not shown]
[figure not shown]
Today's date: / /

Please provide the information below.		
1. What is the patient's current disease status?	 Moderate	 Severe

1023259 Real-World Impact of RA

Site number	-	Participant ID
-------------	---	----------------

imshealth™
INTELLIGENCE APPLIED.

Please provide the information below.		
2. Please perform a swollen and tender joint examination on your patient using the figure below and record the total number of tender/swollen joints in the appropriate boxes on the right.	Tender Joint Count	Swollen Joint Count

If diagnosis is RA:
 
 
  
Tender ○ Mark If 'none'
 
 
  
Swollen ○ Mark If 'none'
 
 
		
3. Please record the most recent Erythrocyte Sedimentation Rate (ESR) (in mm/hour) or C-reactive protein (CRP) (in mg/L) of this patient.	 ESR (mm/hour) Test Date (DD/MM/YYYY): ____/____/_____	
	 CRP (mg/L) Test Date (DD/MM/YYYY): ____/____/_____	
4. Please record the latest DAS28 score*, if calculated		

* For calculation instruction, please refer to study protocol, page 21, clinical case report form (CRF).

1023259 Real-World Impact of RA

Site number	-	Participant ID
-------------	---	----------------

5. Please check all the surgeries this patient has received for her/his Rheumatoid Arthritis since the last completed survey.

 No surgery performed			
 Yes →	Type of Surgery (Please input the number of the list below)	Length of Stay*	Date of surgery (DD/MM/YYYY)
 1	_____	_____ days	____/____/____
 2	_____	_____ days	____/____/____
 3	_____	_____ days	____/____/____
 4	_____	_____ days	____/____/____
 5	_____	_____ days	____/____/____

List of common surgeries for rheumatoid arthritis:

1. Arthroscopy
2. Carpal tunnel release
3. Cervical spinal fusion
4. Total knee replacement
5. Total hip replacement
6. Knee arthrodesis (fusion)
7. Hip arthrodesis (fusion)
8. Synovectomy
9. Other: _____

* For day surgeries, please input 0 days.

6. Please check any Hylan G-F 20 (Synvisc) injections this patient has received for her/his Rheumatoid Arthritis since the last completed survey.

 No injection performed			
 Yes →	Injection Place	Dosage	Number of shots
	 Hip	_____ ml	_____
	 Knee	_____ ml	_____

1023259 Real-World Impact of RA
_____ - _____
Site number Participant ID

7. Please check any adalimumab (Humira) injection this patient has received for her/his Rheumatoid Arthritis since the last completed survey.		
 No, no injection performed		
 Yes →	Dosage	Number of Times
	_____ mg	_____
Administration stop date (if stopped)	____/____/_____ (DD/MM/YYYY)	

1023259 Real-World Impact of RA

Site number	-	Participant ID
-------------	---	----------------

8. Please record all of the medications this patient has received for her/his Rheumatoid Arthritis since the last completed survey			
Drug Name	Average number of pills per day	Dose strength	Times per month
Disease Modifying Antirheumatic Drug (DMARD)			
 ₁ Auranofin (Ridaura, Myochrysine)	_____	_____ mg	_____
 ₂ Azathioprine (Imuran)	_____	_____ mg	_____
 ₃ Cyclosporine (Sandimmune and Neoral)	_____	_____ mg	_____
 ₄ Hydroxychloroquine (Plaquenil)	_____	_____ mg	_____
 ₅ Leflunomide (Arava)	_____	_____ mg	_____
 ₆ Methotrexate (Rheumatrex, Folex)	_____	_____ mg	_____
 ₇ Minocycline (Minocin, Dynacin and Vectrin)	_____	_____ mg	_____
 ₈ Sulfasalazine (Azulfidine)	_____	_____ mg	_____
 ₉ Others	_____	_____ mg	_____
Anti-inflammatory Drug (NSAID)			
 ₁₀ Ibuprofen (Advil, Motrin, Nuprin)	_____	_____ mg	_____
 ₁₁ Naproxen (Naprosyn, Anaprox, Aleve)	_____	_____ mg	_____
 ₁₂ Celecoxib (Celebrex)	_____	_____ mg	_____
 ₁₃ Aspirin (ASA)	_____	_____ mg	_____
 ₁₄ Diclofenac (Voltaren)	_____	_____ mg	_____
 ₁₅ Indomethacin (Indocid)	_____	_____ mg	_____
 ₁₆ Others	_____	_____ mg	_____
Others			
 ₁₇ Steroids	_____	_____ mg	_____
 ₁₈ Stomach or gastric medications	_____	_____ mg	_____

Thank you for completing the Clinician Case Report Form.
Please return this form to the IMS representative.

Appendix D. Health Assessment Questionnaire Disability Index (HAQ DI)**HEALTH ASSESSMENT QUESTIONNAIRE (HAQ-DI)®**

Name: _____

Date: _____

Please place an "x" in the box which best describes your abilities OVER THE PAST WEEK:

	WITHOUT ANY DIFFICULTY	WITH SOME DIFFICULTY	WITH MUCH DIFFICULTY	UNABLE TO DO
DRESSING & GROOMING				
Are you able to:				
Dress yourself, including shoelaces and buttons?				
Shampoo your hair?				
ARISING				
Are you able to:				
Stand up from a straight chair?				
Get in and out of bed?				
EATING				
Are you able to:				
Cut your own meat?				
Lift a full cup or glass to your mouth?				
Open a new milk carton?				
WALKING				
Are you able to:				
Walk outdoors on flat ground?				
Climb up five steps?				

Please check any AIDS OR DEVICES that you usually use for any of the above activities:

 Devices used for Dressing (button hook, zipper pull, etc.)	 Built up or special utensils	 Crutches
	 Cane	 Wheelchair
 Special or built up chair	 Walker	

Please check any categories for which you usually need HELP FROM ANOTHER PERSON:

 Dressing and grooming	 Arising	 Eating	 Walking
--	----------------------------------	---------------------------------	----------------------------------

Please place an "x" in the box which best describes your abilities OVER THE PAST WEEK:

	WITHOUT ANY DIFFICULTY	WITH SOME DIFFICULTY	WITH MUCH DIFFICULTY	UNABLE TO DO
HYGIENE				
Are you able to:				
Wash and dry your body?				
Take a tub bath?				
Get on and off the toilet?				
REACH				
Are you able to:				
Reach and get down a 5 pound object (such as a bag of sugar) from above your head?				
Bend down to pick up clothing from the floor?				
GRIP				
Are you able to:				
Open car doors?				
Open previously opened jars?				
Turn faucets on and off?				
ACTIVITIES				
Are you able to:				
Run errands and shop?				
Get in and out of a car?				
Do chores such as vacuuming or yard work?				

Please check any AIDS OR DEVICES that you usually use for any of the above activities:

 Raised toilet seat	 Bathtub bar	 Long-handled appliances for reach
 Bathtub seat	 Long-handled appliances in bathroom	 Jar opener (for jars previously opened)

Please check any categories for which you usually need HELP FROM ANOTHER PERSON:

 Hygiene	 Reach	 Gripping and opening things	 Errands and chores
----------------------------------	--------------------------------	--	---

Your ACTIVITIES: To what extent are you able to carry out your everyday physical activities such as walking, climbing stairs, carrying groceries, or moving a chair?

COMPLETELY MOSTLY MODERATELY A LITTLE NOT AT ALL

				
--------------------------	--------------------------	--------------------------	--------------------------	--------------------------

Your PAIN: How much pain have you had IN THE PAST WEEK?

On a scale of 0 to 10 (where zero represents "no pain" and 10 represents "worst pain imaginable"), please mark the number below.

0	1	2	3	4	5	6	7	8	9	10
---	---	---	---	---	---	---	---	---	---	----

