9.2.4.7 Study Documents

Clinical case report form (CRF)

The clinical CRF will document the patient's current status (moderate, severe RA), Disease Activity Score in 28 joints (DAS28), prior and current treatments and other relevant clinical and demographic data to be used in segmenting the population during analysis.

To calculate the DAS28 the physician or specialist nurse will:

1. Count the number of swollen joints (out of the 28)
2. Count the number of tender joints (out of the 28)
3. Take blood to measure the erythrocyte sedimentation rate (ESR) or C reactive protein (CRP); the latest measurement in the medical records may also be used if a blood draw is not standard for that visit
4. Ask the patient to make a 'global assessment of health' which will be indicated by marking a 10 cm line between very good and very bad

The physician or specialist nurse will then mark each component score on the CRF and the DAS28 score if calculated (an online scoring calculator for the DAS28 can be found at <http://www.das-score.nl/das28/DAScalculators/dascalculators.html>).

The DAS28 will be scored using the following formula:

$$\text{DAS28 ESR} = 0.56 * \text{sqrt}(\text{tender28}) + 0.28 * \text{sqrt}(\text{swollen28}) + 0.70 * \ln(\text{ESR}) + 0.014 * (\text{Global assessment of Health in cm})$$

$$\text{DAS28 CRP} = 0.56 * \text{sqrt}(\text{tender28}) + 0.28 * \text{sqrt}(\text{swollen28}) + 0.36 * \ln(\text{CRP}) + 0.014 * (\text{Global assessment of Health in cm}) + 0.96$$

DAS28 scores will be interpreted using the following categorization:

- Remission: DAS28 \leq 2.6
- Low Disease activity: $2.6 < \text{DAS28} \leq 3.2$
- Moderate Disease Activity: $3.2 < \text{DAS28} \leq 5.1$
- High Disease Activity: DAS28 > 5.1

The full CRF is presented in Appendix C.

PRO questionnaires

The following PRO questionnaires will be included in the patient questionnaire packet.

Health Assessment Questionnaire Disability Index (HAQ DI)

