#### **3.5.2      *Exposure/Independent Variables of Interest***

- **Patient demographics (if data available)**

- Date of birth
- Age at baseline
- Age groups
- Gender at birth
- Marital status (married, unmarried)
- Medical plan type
  - ✓ The type of healthcare plan each patient is enrolled in at baseline will be determined, including National/Public insurance, Private insurance, Employer benefits, and Other

- **Clinical characteristics**

- Initial Diagnosis of Rheumatoid Arthritis (RA)
  - ✓ Year of initial diagnose
- Initiation of Adalimumab
  - ✓ First time administration (DD/MM/YYYY)
  - ✓ Dosage of first injection (in mg)
- Disease status of RA
  - ✓ Moderate (defined as Disease Activity Score in 28 Joints (DAS28) between 3.2 and 5.1)
  - ✓ Severe (DAS28>5.1)
- Erythrocyte sedimentation rate (ESR) (in mm/hour)
- C reactive protein (CRP) (in mg/L)
- Disease Activity Score in 28 joints (DAS28)

To calculate the DAS28, the physician or specialist nurse will:

1. Count the number of swollen joints (out of the 28)
2. Count the number of tender joints (out of the 28)
3. Take blood to measure the erythrocyte sedimentation rate (ESR) or C reactive protein (CRP); the latest measurement in the medical records may also be used if a blood draw is not standard for that visit
4. Ask the patient to make a ‘global assessment of health’ which will be indicated by marking a 10 cm line between very good and very bad

The physician or specialist nurse will then mark each component score on the CRF and the DAS28 score if calculated (an online scoring calculator for the DAS28 can be found at <http://www.das-score.nl/das28/DAScalculators/dascalculators.html>).

The DAS28 will be scored using the following formula:

$$\text{DAS28} = 0.56 * \text{sqrt}(\text{tender28}) + 0.28 * \text{sqrt}(\text{swollen28}) + 0.70 * \ln(\text{ESR or CRP}) + 0.014 * (\text{Global assessment of Health})$$

DAS28 scores will be interpreted using the following categorization:

- ✓ Remission: DAS28  $\leq$  2.6
- ✓ Low Disease Activity:  $2.6 < \text{DAS28} \leq 3.2$
- ✓ Moderate Disease Activity:  $3.2 < \text{DAS28} \leq 5.1$
- ✓ High Disease Activity: DAS28  $> 5.1$
- comorbidities
  - ✓ Myocardial infarction
  - ✓ Congestive heart failure
  - ✓ Peripheral vascular disease
  - ✓ Cerebrovascular disease
  - ✓ Dementia
  - ✓ Chronic pulmonary disease
  - ✓ Connective tissue disease
  - ✓ Ulcer disease
  - ✓ Mild liver disease
  - ✓ Diabetes
  - ✓ Hemiplegia

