#### **5.5 Analysis Plan for Additional Secondary Objectives**

- Descriptive statistics will be presented for post-index overall RA related direct healthcare resource utilization (Excel Table 8)

- Consultations/visits to healthcare professionals for treatment of RA (number of patients with  $\geq 1$  visit; categorized by the treatment department listed in 3.5.4)
- Procedures received when visiting the healthcare professional(s) for treatment of RA (number of patients with  $\geq 1$  procedure; categories listed in 3.5.4)
- surgeries received when visiting the healthcare professional(s) for treatment of RA (number of patients with  $\geq 1$  surgery; categories listed in 3.5.4)
- Hospitalizations in relation to RA (number of patients with  $\geq 1$  admission)
- Length of stay in days (mean, SD, median)
- Concomitant medications taken for RA (number of patients with  $\geq 1$  medication; categories listed in 3.5.4))

- Associations between disease severity (measured by DAS28) and PROs (HAQ DI score, SF-36 domain scales, EQ-5D-3L index, WPAI outcomes) will be analyzed using the bivariate linear regression model (Excel Table 9.1). Separate models will be estimated to identify the association between DAS28 and each of the PROs.
- Additionally, in Excel Table 9.2, separate bivariate liner regression models will be estimated to identify the association between change in DAS28 and change in each of the PROs at 12 and 24 weeks after baseline respectively.

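### The three clinician forms have no field for the patient's global assessment or the DAS28 version, so a blank DAS28 cannot be computed exactly and an entered one can be checked only approximately

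*Protocol*

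**What the plan says.** Protocol 9.2.4.7 names four DAS28 components: swollen count, tender count, ESR or CRP, and a patient global assessment "indicated by marking a 10 cm line between very good and very bad". It then states: "The physician or specialist nurse will then mark each component score on the CRF and the DAS28 score if calculated". It gives separate ESR and CRP formulas, both with the global term in cm. Table 1 schedules DAS28 at baseline, Week 12, Week 24 and early termination.

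The forms collect less than that. The baseline CRF asks for the two joint counts (item 3), then "4. Please record the most recent Erythrocyte Sedimentation Rate (ESR) (in mm/hour) or C-reactive protein (CRP) (in mg/L) of this patient", with separate dated boxes for each marker, then, as item 5, "Please record the latest DAS28 score*, if calculated". The follow-up CRF runs the same way in items 2 to 4, ending "4. Please record the latest DAS28 score*, if calculated". Items 2 to 4 of the clinician Early Termination Form repeat the sequence.

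SAP 3.5.2 gives a single formula that also contains the global term, with no unit, and applies 0.70 to the log of either marker. SAP 5.2 tabulates baseline DAS28 categories. SAP 5.5 regresses the PROs on DAS28 and adds that "separate bivariate liner regression models will be estimated to identify the association between change in DAS28 and change in each of the PROs".

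**The concern.** The protocol promises a recorded component that its own forms cannot hold. The patient packet does not supply it either: the HAQ has a pain scale and an activities item, the EQ-5D has a 0-100 health scale, and neither document links any of these to DAS28.

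The version is a separate gap. The protocol allows either, the two formulas give different numbers for the same patient, and no form records which one a site used. The score field also has no date, so the latest score need not rest on the marker value printed above it.

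At stake are the association models in Tables 9.1 and 9.2, the baseline DAS28 categories, and any DAS28-based severity factor in the sensitivity ANOVA and Table 10. SAP 3.5.5 imputes only PRO items and partial dates, so a patient with a blank score leaves the DAS28 models. If the version changes between visits, the difference between formulas enters Table 9.2 as change in disease activity.

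**Working it through.** The plan states no figure for this point, so there is none to reproduce. The check is a reading of the forms, followed by sizing.

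**Forms.** Item numbering is continuous on all three (baseline 1-11, follow-up 1-8, early termination 1-8). No numbered item is missing, and none asks for a global assessment or a version.

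**Formulas.** T and S are tender and swollen counts, G the global assessment.
- Protocol, ESR version: 0.56√T + 0.28√S + 0.70 ln(ESR) + 0.014 G
- Protocol, CRP version: 0.56√T + 0.28√S + 0.36 ln(CRP) + 0.014 G + 0.96
- SAP: 0.56√T + 0.28√S + 0.70 ln(ESR or CRP) + 0.014 G

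**Size of the missing term.** With G in cm (0-10), the maximum is 0.014 × 10 = 0.14. On a 0-100 scale it would be 0.014 × 100 = 1.4. The moderate band is 5.1 - 3.2 = 1.9 wide.

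**Size of the version difference.** Joint counts and G cancel, leaving 0.70 ln(ESR) - 0.36 ln(CRP) - 0.96. The documents give no marker values, so these are assumed, with CRP fixed at 10 mg/L (0.36 ln 10 = 0.829):
- ESR 10: 1.612 - 0.829 - 0.96 = -0.18
- ESR 20: 2.097 - 0.829 - 0.96 = 0.31
- ESR 30: 2.381 - 0.829 - 0.96 = 0.59

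A stable patient at the last pair, scored by ESR at baseline and by CRP at Week 12, would show a fall of 0.59 in Table 9.2.

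**Can the version be recovered from an entered score?** Assume T = 10, S = 8, ESR 30, CRP 10. The joint terms give 1.77 + 0.79 = 2.56. Before G, the ESR version is 2.56 + 2.38 = 4.94 and the CRP version 2.56 + 0.83 + 0.96 = 4.35.
- G in cm: 4.94-5.08 against 4.35-4.49. These do not overlap, so the entered value identifies its version.
- G on 0-100: 4.94-6.34 against 4.35-5.75. These overlap.

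In cm the ranges overlap only when the versions differ by 0.14 or less.

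**Category.** With the same joint counts and assumed ESR 40 and CRP 20, the versions give 5.15 and 4.60 before G: high against moderate activity.

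**SAP against protocol formula.** Assume T = 4, S = 4, CRP 5. The joint terms give 1.12 + 0.56 = 1.68. The protocol's CRP version is 1.68 + 0.58 + 0.96 = 3.22 before G; the SAP formula with CRP is 1.68 + 1.13 = 2.81. These fall on opposite sides of 3.2, so central computation would depend on which document is followed.

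**The case against.** Three of the four components are on the forms, and the ESR and CRP boxes are separate and dated. If one box is filled, the version can normally be inferred. If both are filled and G is in cm, the entered score usually reveals it. A reader might infer that DAS28 cannot be verified at all; the documents do not support that. What remains is that inference can fail when the two versions lie close together, when G was on another scale, or when the latest score used other values.

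A reader might also take 1.4 points as the size of the missing term. That needs a 0-100 scale, which neither document states. The SAP formula omits the unit, but the SAP also describes a 10 cm line.

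The baseline exposure is limited. DAS28 is an entry criterion, and Protocol 9.2 requires eligibility evidence in source, so a never-calculated baseline score is unlikely, though the CRF box may still be blank. The baseline CRF also asks for Moderate or Severe status, a fallback for the severity factor. At follow-up that item still offers only those two levels, so it cannot show low activity or remission.

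SAP 3.5.5 already provides for available-data analysis with missing counts, and SAP 5.2 has a missing category for baseline DAS28. That makes the loss visible but does not prevent it, and it says nothing about version.

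Finally, the joint diagrams were not visible in the copy I read, so an unnumbered line on the forms cannot be wholly excluded. The follow-up form's diagram captions survive and show none.

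**Conclusion.** The contradiction between Protocol 9.2.4.7 and the three forms stands and should be corrected. A blank score cannot be computed exactly. An entered score can be checked to within 0.14 if G is in cm, the version is known and the recorded values were the ones used. The unrecorded version is the larger problem: about -0.18 to 0.59 over the assumed ESR range of 10 to 30 at CRP 10, with other marker values giving other differences. How often scores are blank or versions switch cannot be judged from the documents.

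The effect falls on the additional secondary associations, the baseline DAS28 categories and any DAS28-based severity factor. It does not reach the primary result: the paired t-test on HAQ DI change does not use DAS28.

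**What to change.** 1. Add to the baseline CRF, follow-up CRF and clinician Early Termination Form a field for the global assessment with its unit, and a tick box for the ESR or CRP version.
2. For patients already seen, query sites for both from source where available, through the query process in Protocol 9.8.2. Data collection was planned to end on 28 February 2018, so for this study the query and the SAP rule probably matter more than the form edit.
3. In the SAP, first reconcile the formula in 3.5.2 with Protocol 9.2.4.7: 0.70 on the log of either marker with no constant, against 0.36 ln(CRP) + 0.96 for the CRP version. State the unit of the global term.
4. Then compute DAS28 centrally from components, with the same version at all visits for a patient. Report as missing, with counts, any score whose components or version cannot be retrieved.

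The assessment is already required, so no procedure is added. The cost is a small form edit and up to one query per visit, at most 89 × 3 = 267 over the scheduled visits if all 89 patients are enrolled. Some queries may not be answerable from routine-care records.
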